## **INNOVATION**

- This study will novelly assess the effects of the SREC (and potentially other newly available product) aerosols directly in human lungs of smokers who completely substitute the SREC for smoking, and compare this to quitting with NRT.
- The extended use over 10 weeks (8 week intervention) on product that will allow for the subject to learn how to use the product and adjust to adverse effects for two weeks (if any) that are generally short-lived, and allow the lungs to respond over 8 weeks.
- Conducting a trial with serial bronchoscopies before and after the use of the SREC device allows for within-subject comparisons as well as including comparisons to a randomly assigned group.

- The use of multiple endpoints for gene expression (mRNA and miRNA), metabolomics, cell and cytokine changes are comprehensive and complementary. This allows for an integrated assessment for multiple ways that inflammation can happen to distinguish treatment effects.
- This study uses 'omics to assess inflammation, which also provides data for other disease pathways.
- This study will provide new data for the effects of nicotine on pulmonary inflammation using a device demonstrated to deliver nicotine at levels similar to cigarettes.

#### 4. Methods

**Figure 1: Study Overview**

\*Cessation counseling will be provided at visits and calls for all intervention groups. Subjects may also proactively contact study staff for additional support.

## a. Study Design

### i. Study arms/groups

Participants will be randomized to one of four groups of subjects (n=32 for each group): controls who will continue to smoke their usual brand, a group who will switch completely to the SREC with nicotine, a group who will switch completely to the SREC placebo, and a group who will stop smoking using nicotine replacement therapy (NRT).

### ii. Randomization process

Participants will be randomized to one of four groups. This design allows for a rolling admission and increased contemporary controls in the event a device is not available at the time of enrollment. The conditions subjects are randomized to may vary depending on product availability. Within each group, we will also randomize the patients to sequence the right or left lung for the baseline bronchoscopy in an approximate 1:1 ratio. These patients will then receive a second bronchoscopy in the opposite lung at ~71 days in order to reduce the influence of the baseline procedure at follow-up. The randomization procedures will be supervised by the biostatistician.

### iii. Intervention type/process

This study is a 10-week clinical trial (8 weeks on the experimental condition after a scheduled quit date; n=128) for healthy smokers randomized to one of four groups. The duration for the intervention period has been extended from 4 to 8 weeks to harmonize with two other NIDA grantees who are studying the SREC, at the request of NIDA. An overview is shown in **Figure 1**. Each group is 32 subjects. All subjects will undergo a baseline bronchoscopy. Bronchial brushings and BALs will be collected during the bronchoscopies to assess total and differential cell counts, inflammatory cytokines, mRNA gene expression, miRNA expression, genome methylation, microbiomes, proteomics, CyTOF, pulmonary function tests and BAL metabolomics. Subjects also will be assessed for THC exposure, exhaled FeNO, exhaled CO, and urinary PG and glycerin.

At the baseline bronchoscopy visit, subjects will be randomized to either one of the four groups (control and interventions). The SREC intervention groups will be instructed on how to use their assigned product and after the visit begin to use the device daily and will be allowed to continue smoking, in order for them to learn how to use the device. They will be told that after two weeks of use to begin their assigned condition, essentially establishing a smoking quit date (e-cig-only) on day 15. To mediate withdrawal symptoms and increase retention, subjects assigned to SREC placebo group will be offered varenicline at no cost, and used according to FDA indications. Those participants will be given the medication at the day 8 visit, one week before the day 15 quit date. The NRT group will begin to use the NRT one week before the day 15 quit date. This design allows for a rolling admission and increased contemporary controls in the event a device is not available at the time of enrollment. The conditions subjects are randomized to may vary depending on product availability.

After 10 weeks of their assigned condition (+/- 3 days), subjects will undergo a second bronchoscopy as described above. Subjects assigned to the nicotine-SREC or placebo-SREC conditions will undergo inhalation assessment. In an effort to standardize the timing and recent product exposure, subjects be instructed to use the device immediately prior to the visit. Subjects who report the device was not used as instructed will be asked to use the device before proceeding with the visit. Subjects assigned to the nicotine-SREC condition will also undergo a nicotine boost assessment that includes two blood draws, one prior to and one after a timed use session.

Subjects assigned to the control condition (smoking their usual brand) will undergo all the procedures as the other conditions, except the nicotine boost and inhalation assessment. The specific value using controls to users, rather than only assessing within subject changes for pre- to post-bronchoscopy biomarkers, is our ability to evaluate the impact of being enrolled in a smoking study, e.g., smokers in the control group might reduce their exposures because they are enrolled in a smoking study.

A biorepository of the lung samples, saliva, urine, blood, nasal lavage and nasal brushings will be established. A Data and Safety Monitoring Board will be established as described below.

## **b. Participant Selection**

### **Eligibility Criteria**

- Male or female subjects who are age 21-52\*;
- Smokers who smoke  $\geq 5$  filtered cigarettes/day for  $\geq 1$  year\*;
- No unstable or significant medical conditions as determined by medical history (see exclusion criteria below) to ensure safety of the subject, to minimize the effects of poor health on biomarker measures and to maximize compliance to study procedures);
- Negative COVID-19 test (if applicable)\*\*;
- Subject has an electronic device and is willing to download the iCO app to report exhaled CO level daily;
- Able to read adequately to complete the survey and related study documents or give consent; and,
- Subject has provided written informed consent to participate in the study.

### **Exclusion Criteria**

- Regular consumption of hand rolled cigarettes (i.e., a machine is not used to standardize the process);
- Immune system disorders requiring medication;
- Prior diagnosis of chronic pulmonary disease (e.g., asthma with regular use of medications, COPD, chronic bronchitis, and restrictive lung disease);
- Acute bronchitis or pneumonia within 1 year;
- COVID-19 diagnosis or related symptoms within the last 3 months\*\*;
- Reported history of diagnosed kidney or liver disease;
- Any medical disorder that will increase the risk from bronchoscopy, affect biomarker data (i.e., cancer), or increase risk of an adverse effect from e-cig use;
- General anesthesia within 1 year;
- Regular use of inhalant medications in the last 3 months;
- Use of antibiotics in prior 30 days;
- Use of steroids, including corticosteroids, in prior 30 days;
- Allergies to study medications, such as, lidocaine, Versed, Fentanyl or Cetacaine;
- Allergies to propylene glycol/ glycerin or flavors;
- History of hypersensitivity to varenicline;
- Bronchoscopy or any other lung procedure for any reason within the previous 6 months;
- Current or recent (within three months) alcohol or drug abuse problems;
- Regular use of an e-cigarette or other combustible tobacco products in the prior 3 months (not to exceed 10 times and no use within 2 weeks) - subjects will be asked to refrain from using marijuana and all other tobacco products while active in the study (however, use is not an exclusion);
- Currently using nicotine replacement or other tobacco cessation products (to minimize confounding effects of another product) or intention to quit in next three months;
- History of bronchospasm or adverse reaction to previous e-cig use;
- BMI > 40 (risk of unstable airway);
- Pregnant or breastfeeding in prior 3 months- If the subject is female, a urine pregnancy test at no cost to the subject will be done on the day of bronchoscopy\*\*\*;
- Subject does not have an electronic device or is unwilling use the iCO app to report exhaled CO; and
- Unable to read for comprehension or completion of study documents.

\* Age and number of cigarettes smoked per day increases the participant pool and generalizability.

\*\* According to institutional standards, which may evolve throughout the study, if a subject self-reports testing positive for COVID-19, the condition should be resolved without ongoing symptoms for at least three months. If a subject tests positive before the first bronchoscopy, the subject would be placed on a wait list for at least three months and re-tested before his/her appointment; if a subject tests positive before a follow-up bronchoscopy, his/her participation will be withdrawn by the PI.

\*\*\* All females of child-bearing potential (i.e., not postmenopausal or surgically sterile) will provide a spot urine sample to be used for a urine pregnancy test. Research staff will read the test result and document positive or negative in the CRF. All females of child-bearing potential must agree not to become pregnant and to use an approved form of birth control (birth control pills, implants, IUD, Depo-Provera, or double barrier method (e.g. condoms and diaphragm)) while participating in the study.

All subjects are screened by a pulmonologist obtaining a medical history and a physical examination (heart, lungs and oral cavity) to ensure no increased risk from bronchoscopy or e-cig use.

#### **i. Recruitment Procedures**

Subjects will be recruited from advertisements through a variety of media outlets and the internet, as well as community events, and including Research Match, Study Search and a registry of subjects interested in future tobacco studies, such as (2014C0030). This latter important source for identifying subjects is currently conducting a mailing to 170,000 homes in Franklin County and southern Ohio to identify subjects for three of the current P50 projects (OSU 2014C0030); families who return the mailings agree to be contacted for future studies, and the returned surveys will identify smoking status. Thus, for subjects not selected for existing P50 projects, they can be contacted for this study.

Subjects will also be recruited through respondent-driven sampling (RDS), which is commonly used in studies involving contact tracing and social networks (e.g., sexual health studies). This sampling method is a type of peer-driven chain-referral sampling (Heckathorn 1997, 2002). Although there are biases associated with chain-referral sampling that can affect the composition of the sample achieved, RDS can control these biases through its methods of data collection and analysis. RDS initial recruiters who are study subjects will recruit future subjects (seeds) who in turn recruit other subjects (seeds). This chain of recruiters and recruits then continues for multiple “waves” of recruitment. Ongoing recruitment is fostered with a dual incentive system: one incentive for participating in the project and another incentive for each person recruited. Recruiters are linked to their seeds by a unique number or code on recruitment coupons/flyers, and they are limited in how many people they can recruit. The identity and status of individuals who may have provided RDS codes/coupons will not be disclosed. The seeds who meet the basic criteria (current smoker, age 21 or older, willing to be screened) can choose to participate in the study or not. Referring individuals to the study is optional. Subjects’ participation in the study will not be affected if they do not invite others or if those they may invite do not meet the criteria outlined above.

The various approaches used for this study will foster recruitment across a spectrum of education and socioeconomic status, and race/ethnicities.

The advertisements would read as follows:

*“Cigarette smokers (age 21-52) are needed for a research study to help understand the effects of using electronic cigarettes on the lungs. Volunteers should be willing to undergo two medical procedures called a bronchoscopy. Volunteers may be asked to continue to smoke their own cigarettes, use electronic cigarettes or quit smoking using nicotine replacement therapy. Volunteers may earn over \$1,100 for completion of the study.”*

Advertisements may also include the following statements:

- \* Marijuana users will be permitted to enroll in the study
- \* Volunteers will not be excluded for using any form of marijuana (e.g., smoking marijuana).

Information Warehouse: Subjects will also be recruited using data from the Information Warehouse (IW) to identify potential participants and providers. The IW will be petitioned to query the electronic medical records for patients seen within the last 12 months by an OSU provider. Subjects will be:

- Current smoker;
- Age 21-52;
- Absent of medical conditions (COPD, chronic bronchitis, restrictive lung disease, kidney or liver disease);
- BMI <40;
- Live in Columbus or surrounding areas (Counties: Franklin, Delaware, Morrow, Marion, Union, Hardin, Logan, Madison, Champaign, Clark, Madison, Fayette, Pickaway, Ross, Fairfield, Hocking, Perry, Licking, Muskingum, Coshocton, and Knox).

The IW request will also include the patient's provider and the patient's contact information and their EMR number to track the patient's vital status.

The PI will contact providers identified by the IW asking for their permission to send a dually signed recruitment letter introducing the study. Upon receiving provider permission, study staff will prepare the letter and send to the patient. The provider will not be engaged in research. His/her involvement will be limited to allowing study staff to send a recruitment letter after provider approval. Study staff will send the initial letter and a follow-up letter approximately 30 days after if no contact is initiated. The letter(s) may also be sent electronically if an email address is provided by the IW. Two versions of the initial recruitment letter will be available based on the provider's preference: 1) patients can opt out and study staff will wait at least 7 days after the letter is mailed to contact the patient by phone; or 2) patients can opt in and study staff will only call patients who initiate contact.

My Chart: In addition to the IW, this study may recruit through My Chart. Subjects will be:

- Active MyChart users;
- Smokers;
- Men and women;
- Age 21-52;
- Absent of medical conditions (COPD, chronic bronchitis, restrictive lung disease, kidney or liver disease);
- BMI <40;
- Live in Columbus or surrounding areas (Counties: Franklin, Delaware, Morrow, Marion, Union, Hardin, Logan, Madison, Champaign, Clark, Madison, Fayette, Pickaway, Ross, Fairfield, Hocking, Perry, Licking, Muskingum, Coshocton, and Knox).

Social Media: Social media platforms such as Facebook, Instagram, YouTube, etc. will be used to recruit users from Columbus and surrounding areas (up to 100 miles) ages 21-52 years interested in smoking. OSUCCC Marketing will host a landing page linked to the social media videos. Ads will be linked to a landing page (<http://go.osu.edu/srec-study>). Those interested in the study may directly contact study staff or request more information by completing a short questionnaire and providing contact information, age, and number of cigarettes smoked per day. An automatic email will be sent to the study team who will contact the subject to provide more information about the study and schedule an orientation visit as needed. As part of their routine tasks, OSUCCC Marketing will monitor the account including the SREC study posts daily and respond to any comments. When responding to comments, OSUCCC Marketing will direct users to the landing page or study personnel to answer questions.

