Clinical studies and case reports have studied the acute health effects of e-cigs on humans, which until recently have been considered mild [236-239]. However, while there have been scattered case reports over the last 5 years of serious pulmonary toxicity [240-243] ([https://www.cdc.gov/tobacco/basic\\_information/e-cigarettes/severe-lung-disease.html](https://www.cdc.gov/tobacco/basic_information/e-cigarettes/severe-lung-disease.html)), a relationship to e-cig use has been unclear. In the past 6 months, clusters of cases are now appearing across the U.S., and have included deaths. The causes are under active investigation and so the nature of the respiratory illness is unclear, and to date no single device or contaminant has been found. The majority of patients have reported vaping cannabis oil, such as THC, obtained on the black market or other sources. In addition, one of the chemicals that has been possibly linked to the addition of is Vitamin E acetate to e-liquid cartridges and pods (tocopheryl acetate). Many of the respiratory illnesses resemble lipid pneumonia and laboratory studies suggest disorders of lipid homeostasis [244]. Bronchoscopies of healthy e-cig users also point to altered lipid homeostasis and matrix proteins [245, 246]. These clusters of cases have now led the FDA and CDC to advise consumers to protect themselves by not starting to use e-cigs and especially not using vaping products of any kind obtained off the street or black market and to refrain from using THC oil or modifying/adding any substance to vaping products purchased at stores. (Our study will now include explicit warnings about this, including the advice to not alter any commercial products.) Explicit recommendations by the FDA and CDC have not advised smokers to stop using commercial and unaltered e-cigs. Investigations continue to focus on adulterated products and contaminants. Also, whether these illnesses represent idiosyncratic and rare reactions or are bell-weather responses to a more general and long term chronic health effect is unknown. (And needs to be considered in the context if e-cigs can help smokers quit, albeit risks that exist much like any medical treatment including smoking cessation drugs.) The implication is that these new reports represent some recent change in devices or how they are used, and that existing commercial products are not associated with these serious and rare respiratory effects. Thus, studies such as this protocol have the potential to provide important information about health e-cig users.

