NRT if the appointment is postponed. At the next visit, the participant will return unused NRT, which will be recorded and redispensed as appropriate. Subjects will be monitored for adverse reaction using the same process as all other arms. The NRT will be distributed assuming the maximum allowed per day is 1 patch, 20 lozenges, and 24 pieces of gum.

**Day 8/ Wk1 visit:** One week after the baseline bronchoscopy, subjects will return (day 8) to report their tobacco and/or product use status, and to report any health issue. Subjects will be offered the opportunity to complete the questionnaires online and measure their breath CO within 24 hours before their scheduled visit. Subjects will complete questionnaires, and CO will be assessed. Blood pressure, heart rate, oxygen level and weight will be recorded.

Subjects in the SREC arms will be reminded that after one week of use as they learn to use the product and work towards complete substitution, they will begin their assignment effective on day 15. SREC users will be encouraged to use the product as frequently as needed to address cravings, allowed to smoke their usual brand of cigarettes *ad libitum* for another week, and encouraged to reduce their cigarettes per day to 5 or less, followed by quitting cigarette smoking and avoiding cannabis use. Subjects randomly assigned to the Complete Substitution with the placebo SREC device will be provided with appropriate dose/amount of varenicline and will be instructed to use it as indicated above.

Subjects randomized to NRT complete substitution will be provided patches in combination with gum and/or lozenge unless otherwise discussed, and instructed how to use these products. Dosing will be determined based on their baseline consumption and time to first cigarette. Subjects will be allowed to use a combination of products (e.g., patch and gum/lozenge) in order to achieve cessation. If subjects experience side effects, dosages can be reduced.

All subjects randomized to receive an intervention will receive counseling with motivational interviewing in order to achieve compliance.

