Poisson regression achieves at least 80% power to detect a mutation rate ratio of 2.1 between the sample origins considering a significance threshold of 0.01 and 84 paired samples. For mtDNA CN, a two-sided paired t-test achieves 80% power to detect a mean of paired differences of 0.4 standard deviations of the paired differences considering 84 paired samples and a significance threshold of 0.01. Correlations (CN) and Cohen's kappa (mutational burden) will also be calculated between the two tissues for each of the assays.

- 7) As a secondary aim, we will test if treatment is associated with differences in mtDNA genetic features between tissues. Generalized linear mixed models will be employed with measurement (mtDNA genetic features) as the dependent variable, a random effect for patient, covariables for baseline measure and sample origin, a main effect of arm, and an interaction effect of origin* arm:

$$\text{Feature} = \text{sample\&rand} + \text{baseline} + \text{origin} + \text{arm} + \text{arm*origin} + e.$$

This analysis will investigate whether treatment is associated with differences between tissues. The interaction term will be comprised of four groups of 21 for each pair of arms.

To conservatively estimate the power to detect this interaction effect, the power will be calculated while adjusting the significance threshold for the number of pairwise tests ($n=6$; $p=0.01/6=0.0017$). A two-sided, two-sample t-test achieves 80% power to detect an 1.5 fold difference between any two groups considering a significance threshold of 0.0017, 21 samples per group, and a coefficient of variation of 0.32 [4].

- 8) As an additional exploratory analysis, we will study dose-response associations of cigarette smoking with biomarkers at baseline bronchial and nasal samples separately. Generalized linear models (again, Poisson or Gaussian) will be fit with biomarkers as the dependent variable and covariables (e.g., cigarettes per day [cigs/day] and urinary cotinine levels, separately), adjusting for confounders, such as sex and age. THC use will also be examined.

References

1. Zhang, S., et al., *Empirical comparison of four baseline covariate adjustment methods in analysis of continuous outcomes in randomized controlled trials*. Clin Epidemiol, 2014. **6**: p. 227-35.
2. Julious, S.A., *Sample sizes for clinical trials with normal data*. Stat Med, 2004. **23**(12): p. 1921-86.

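### Cannabis advice is repeated only in the SREC arms' instructions, and the THC assays have no named role in the arm comparisons

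*Protocol*

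**What the plan says.** **Admission.** Protocol 4.b.i allows advertisements to state "Volunteers will not be excluded for using any form of marijuana (e.g., smoking marijuana". The Revision History entry of 05/14/2020 gives the reason: a sample closer to the general population.

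**Rule for everyone.** One bullet of the Exclusion Criteria (Protocol 4.b) first limits "Regular use of an e-cigarette or other combustible tobacco products in the prior 3 months (not to exceed 10 times", with none in the last 2 weeks. It then adds "subjects will be asked to refrain from using marijuana and all other tobacco products while active in the study (however, use is not an exclusion". That request is not tied to any arm.

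**Arm-specific instructions.** In Protocol 4.c.i, the Product use text for e-cig users includes "followed by quitting cigarette smoking and avoiding cannabis use". At the Day 8 visit, SREC users are "encouraged to reduce their cigarettes per day to 5 or less, followed by quitting cigarette smoking and avoiding cannabis use". The NRT paragraphs in the same two places cover product choice, dosing and side effects and do not mention cannabis. No corresponding instruction is written for controls.

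**Measurement.** Table 3 (Protocol 4.d.i) lists marijuana/THC and cannabinoids in blood and urine at both bronchoscopies (BR1 and BR2). Protocol 2 names THC among the exposures used to judge compliance, and Protocol 4.d.iii describes it as a check on abstinence from marijuana.

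**Analysis.** SAP item 2 has an open covariate list whose examples are baseline smoking, FTND and gender. SAP item 3 defines Model 1 as follow-up measure on baseline measure and arm. THC appears once, in the exploratory baseline dose-response analysis of SAP item 8: "THC use will also be examined".

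**The concern.** Randomisation balances cannabis use before allocation. It does not balance what the trial then does differently in each arm. Advice repeated in two arms and not in the other two is a small co-intervention that travels with treatment. If it works, and if cannabis smoke or aerosol raises the lung markers, use falls more in the SREC arms and part of the fall in inflammation is credited to the SREC.

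The direction bears on the main hypothesis in Protocol 2, that switching to e-cigs lowers lung toxicity but by less than quitting with NRT. Such a shift would flatter SREC against continued smoking and narrow its gap to NRT.

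The analysis side matters as well. The data that would reveal the problem are collected in every subject at both bronchoscopies, but the plan does not say how they enter the arm comparisons. That choice would then be made after the data are seen.

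**Working it through.** **Step 1: compare the instructions by arm.**

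| Arm | General request (Exclusion Criteria) | Product use text | Day 8 text |
|---|---|---|---|
| Nicotine SREC | yes | cannabis named | cannabis named |
| Placebo SREC | yes | cannabis named | cannabis named |
| NRT | yes | not named | not named |
| Control | yes | no text | no text |

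In the Product use section, the sentence's own subject is simply the subjects, within a paragraph that opens with e-cig users, so a wider reading is possible there. The Day 8 sentence is explicitly about SREC users. The two SREC arms get the same wording, so the nicotine contrast is not exposed.

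**Step 2: what the analysis does with THC.** Model 1 has no THC term. The open list in SAP item 2 permits one but does not name it. SAP item 8 concerns baseline samples only. No planned analysis is stated for THC at BR2 by arm.

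**Step 3: a yardstick from the plan.** Protocol 4.g.ii assumes 32 × 0.66 = 21.1, so 21 completers per arm, CV 0.26 and two-sided alpha 0.0001, and claims 80% power for a 1.5-fold difference in cell count. On the log scale:

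- SD = √ln(1 + 0.26²) = 0.256
- A two-sample t-test with 21 per arm has 77.7% power at 1.5-fold and reaches 80% at 1.51-fold.

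The plan's figure is reproduced after rounding and is not in dispute.

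**Step 4: possible size, on assumed inputs.** The documents give no cannabis prevalence and no effect of cannabis on any marker. Let d be the between-arm difference in the proportion using cannabis at BR2, and F the fold effect of use on cell count. Then shift = exp(d × ln F).

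| d (assumed) | F (assumed) | Shift in contrast | Power for a true 1.5-fold effect if the shift opposes it |
|---|---|---|---|
| 0 | any | 1.00 | 77.7% |
| 0.10 | 1.25 | 1.02 | 69% |
| 0.10 | 2.0 | 1.07 | 49% |
| 0.20 | 1.25 | 1.05 | 60% |
| 0.20 | 2.0 | 1.15 | 20.5% |
| 0.30 | 1.25 | 1.07 | 50% |
| 0.30 | 2.0 | 1.23 | 5% |

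The last column applies to SREC versus NRT if NRT is truly lower. Against controls the shift would add to an apparent SREC benefit.

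For scale, if 20% to 40% of subjects used cannabis, that is 0.20 × 21 ≈ 4 to 0.40 × 21 ≈ 8 per arm. If half stopped in an SREC arm and none elsewhere, the gap would be 2 to 4 of 21, about 10 to 20 points, and the shift 1.02 to 1.15. If nobody takes up cannabis during the trial, d cannot exceed the share of users at entry.

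**Step 5: what a baseline covariate can do.** The standard deviation of the chance difference in baseline use between two arms of 21 is √(2p(1−p)/21): 0.12 at p = 0.20 and 0.15 at p = 0.40. A BR1 THC term deals with that imbalance and may add precision. It cannot remove a difference that arises after randomisation; only equal instructions prevent that, and only BR2 THC reveals it.

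**The case against.** The strongest reply is that the request to refrain already covers all arms, with no limit on how often it is made, and that the uneven part is one short phrase in two places. Differential use is not shown. Every size above is assumed, and a scenario in which that phrase halves use in one arm while the general request does nothing in another is extreme. Prior use is balanced in expectation, Model 1 adjusts for the baseline marker, and the open covariate list would admit THC. All of this stands, and it limits the point to a possible bias of unknown size. It gives no reason to keep the wording uneven or the THC analysis unstated.

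Three stronger readings are tempting, and the documents do not support them.

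- **The advertisement contradicts the e-cigarette exclusion.** The bullet limits "Regular use of an e-cigarette or other combustible tobacco products in the prior 3 months" and says in the same place that marijuana use does not exclude. There is no exclusion of THC vapers to contradict. What is missing is a statement of whether vaping THC counts toward the e-cigarette limit.
- **Admitting cannabis users conflicts with the protocol's safety warnings.** Protocol 3 does say of the vaping-related illness that "The majority of patients have reported vaping cannabis oil, such as THC". But the same section commits the study to explicit warnings, Protocol 4.b has a pulmonologist screen every subject for added risk, and Protocol 4.f.ii tells those who vape to use only study products and add nothing, THC included. Admission was a deliberate choice.
- **A second inhaled exposure is mixed into the SREC effect.** This would need an arm difference in use, which is not shown. If the extra advice worked, cannabis exposure in the SREC arms would be lower, not higher.

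**Conclusion.** The point holds in a limited form. The arm-specific instructions are uneven in a way that randomisation cannot balance, and THC results collected at both bronchoscopies have no stated role in the arm comparisons. The contrasts exposed are SREC versus control and SREC versus NRT.

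The effect could be nil. Under the assumed ranges it runs from negligible (1.02-fold) to material (1.23-fold) against a 1.5-fold detectable difference. Those figures rest on three assumptions that the documents neither confirm nor exclude: that the repeated advice changes behaviour, that it does so by 10 to 30 points more in the SREC arms, and that cannabis use changes cell count 1.25- to 2-fold. The case for acting rests on the low cost of the remedy, not on a demonstrated bias.

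**What to change.** 1. **Protocol 4.c.i.** Reconcile the Product use and Day 8 text with the general request in the Exclusion Criteria, so that all four arms, controls included, receive the same cannabis wording at the same visits.
2. **SAP items 2 and 3.** Name BR1 THC status as a covariate in Model 1, for precision and chance imbalance, and state which specimen and cut-off define it.
3. **SAP, new line.** Report BR2 THC status by arm. If it differs, add a sensitivity analysis of the SREC-versus-control and SREC-versus-NRT contrasts, labelled as supportive because BR2 status arises after randomisation.
4. **Minor clarification, Protocol 4.b and 4.b.i.** Say whether vaping THC counts toward the e-cigarette limit, and make the optional advertisement wording match. The choice is the sponsor's.

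The cost is a line in the visit script, one extra model term and one descriptive table. No new assay or visit is needed, and the decision to admit cannabis users can stand.
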